1 - **HUMAN SUBJECTS RESEARCH PROTOCOL**

2 **COVER PAGE**

3

4

5

6

7

8 **Official Study Title:** Enhancing Prolonged Exposure with Cannabidiol to

9 Treat PTSD

10

11 **NCT number:** NCT05132699

12

13 **IRB Approval Date:** 11-15-2022

14

15

16 **Unique Protocol ID:** HSC20210711H

17

18

19

20

21

22

23

24

25

26

27

28

29

30

31

32

33

34

35

36

37

38

39

40

41

42

43

44 **1. PROTOCOL TITLE:** Enhancing Prolonged Exposure with Cannabidiol to Treat PTSD45 **2. ABSTRACT**

46 Posttraumatic stress disorder (PTSD) is considered a signature psychiatric disorder among military populations. When left
47 untreated, the symptoms of PTSD can cause significant health and functional impairments. While established treatments
48 for PTSD exist, there remains room for improvement in outcomes since almost half of military patients fail to benefit from
49 treatment. Epidiolex (Cannabidiol [CBD]) is an FDA-approved, non-controlled prescription medication with promising
50 potential for the treatment of PTSD.^{1,2} To date, there are no published clinical trials investigating CBD in reducing PTSD,
51 and existing literature in humans with PTSD only includes healthy individuals or case study data. Greater research is
52 needed to fully understand the benefits of CBD for PTSD and to better understand biological mechanisms for its effect.
53 The primary goal of this pilot project is to demonstrate the safety and feasibility of using CBD in combination with standard
54 of care prolonged exposure (PE) psychotherapy to reduce PTSD symptoms (Aim 1). We will also assess possible
55 biochemical and physiological outcomes associated with treatment (Aim 2) and evaluate the relationship between
56 changes in biochemical/physiological measures with PTSD symptom reductions (Aim 3). To address study aims, we will
57 enroll 24 individuals with PTSD to be randomized to CBD (n=12) or placebo (n=12) and all participants will receive 10
58 daily sessions of PE.

60 **3. OBJECTIVES/SPECIFIC AIMS/RESEARCH QUESTIONS**

61 This project will be a pilot, double-blind randomized controlled trial of CBD effects to pursue three goals: (1) to
62 demonstrate the safety and feasibility of using CBD to reduce PTSD symptoms in conjunction with massed PE (mPE); (2)
63 to assess biochemical and physiological outcomes associated with PTSD treatment; and (3) to evaluate the possible
64 relationship between changes in biochemical/physiological measures with PTSD symptom reductions.

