7. RESEARCH PLAN

7.1 Selection of Subjects

Number of subjects to be screened for eligibility: 40

Target number randomized: 28

Target enrollment number for completers: 24

7.1.1. Subject Population.

Individuals between 18-65 years old recruited from the San Antonio community will be invited to participate in this research.

Efforts will be tailored to equally recruit diverse individuals across sex, gender/sexual orientation, race, age, disability, socioeconomic status, national origin, and branch of military service.

7.1.2. Inclusion and Exclusion Criteria.

Inclusion Criteria

1. Individuals between the age of 18 to 65 years old at time of screening.
2. Able to write, read, and speak English
3. PTSD diagnosis as assessed by Clinician-Administered Posttraumatic Stress Scale (CAPS-5)
4. Stable medication regimen for at least four weeks prior to the onset of study participation.

Exclusion Criteria

1. History of opiate, cocaine, methamphetamine, benzodiazepine, or cannabis abuse as determined by the National Institute of Drug Abuse Quick Screen (NIDA-Q).
2. Currently using opiates, cocaine, methamphetamines, benzodiazepines, or cannabis as evidenced by a positive urine drug screen prior to enrollment.
3. Currently pregnant as determined by a positive urine pregnancy test prior to enrollment.
4. Current clinically significant alcohol abuse in the past two weeks on the Quick Drinking Screen (QDS).
5. Currently breastfeeding.

238 6. Ongoing illness or physical health problem(s) that may be exacerbated by CBD (e.g., history of liver problems)
239 7. History of significant allergic condition, significant drug-related hypersensitivity, or allergic reaction to
240 cannabinoids.
241 8. Regular use of the following concomitant medications because of the possible interaction with CBD
242 • The anti-convulsant/anti-epileptics Carbamazepine and Phenytoin
243 • The atypical antipsychotics Olanzapine, Quetiapine, and Risperidone
244 • The entire class of barbiturates (Sedative-Hypnotics)
245 • Chronic, daily use of any class of benzodiazepines. Intermittent or as needed dose of a benzodiazepine will
246 be allowed.
247 • The miscellaneous hypnotics Zaleplon, Zolpidem, Eszopiclone, Ramelteon, and Suvorexant
248 • The herbal supplement St. John's Wort.
249 • The entire class of glucocorticoids
250 • Use of platelet inhibitors Clopidogrel and Warfarin unless the participant is on a stable dose.
251 • The antiretrovirals Ritonavir and Indinavir

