 346 and matching placebo for this study will be obtained through Oakdell Pharmacy which will obtain a sufficient supply of
 347 CBD for 12 participants from their supplying manufacturer. They will then prepare CBD (n = 12) and matching placebo (n
 348 =12) dosage for 24 participants in blinded containers that will be numbered per the randomization design. The medication
 349 and placebo will be dispensed to a trained study team member and transported in a locked container to the STRONG
 350 STAR Clinic where it will be stored in a locked cabinet until the participant arrives to receive the medication at the
 351 medication review appointment 3 days prior to beginning mPE.

352 Massed Prolonged Exposure (mPE). Prolonged Exposure (PE) is a first-line, empirically supported cognitive behavioral
 353 treatment for PTSD and serves as the foundation for mPE.¹⁶ mPE, delivered daily Monday through Friday over two
 354 weeks, utilizes exposure-based interventions to target psychological mechanisms (i.e., experiential and behavioral
 355 avoidance; maladaptive cognitive changes) that are thought to maintain trauma-related symptoms. Ten 90-minute
 356 sessions of mPE, which has been found to be non-inferior to ten 90-minute spaced PE delivered once or twice a week
 357 over eight weeks, helps minimize military-specific treatment barriers, and decreases treatment dropout rates.¹⁴ For this
 358 study, each participant will receive ten 90-minute mPE daily over two weeks. Up to 19 days following initiation of the
 359 medication regimen will be allowed to complete the ten sessions of mPE to accommodate scheduling constraints.
 360 Consistent with the standard spaced PE therapy manual, mPE includes four primary treatment components: (1)
 361 psychoeducation on common reactions to trauma; (2) relaxation training; (3) in vivo exposure; and (4) imaginal exposures.
 362 In vivo exposure involves approaching avoided situations, people, places, and/or objects that are realistically safe. With
 363 imaginal exposure, participants repeatedly and systematically revisit their trauma memory and related thoughts and
 364 feelings. Participants also will be asked to complete homework, including reviewing treatment materials, listening to
 365 recordings of their imaginal exposure, and completing in vivo exposures. Since mPE requires considerable time and
 366 effort, the study team will work with the participant to receive a release from work while participating in the treatment.

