450 devices are monitored by state-of-the-art monitoring applications that include configuration audit, management, and
451 availability 24x7.

458 The UTHSA STRONG STAR data server is currently a VMware Instance running Windows Server 2016 Enterprise
 459 Standard with daily backup services and vSphere Business Continuity Advanced Failover.

460
 461 Only select STRONG STAR Data and Statistics Services personnel have direct access to the data on a "need to access
 462 basis"; for example (but not limited to) detecting and repairing data corruption and producing reports not currently within
 463 the STRONG STAR system. STRONG STAR Data and Statistics Services also follows the Principles Of Least Privilege
 464 (POLP). All user activity is tracked and recorded within the system so if any records are added, altered, or viewed the
 465 action is recorded and can be recalled for auditing purposes. Access to this information will require a password-protected
 466 login available only to authorized STRONG STAR Data and Statistics Services staff.

467
 468 Every member of the Research Team will be trained and monitored about how to handle and protect both medical and
 469 research records. Furthermore, the Research Team strictly controls access to study data.

470
 471 The STRONG STAR Data Safety and Monitoring Plan (DSMP) that has been developed in accordance with the National
 472 Institutes of Health Office of Human Research Protection to assure the appropriate clinical safety monitoring of study
 473 subjects participating in research will be used to monitor this study.

474 475 7.4. Statistical Consideration

476 477 7.4.1. Sample Size Estimation.

Estimate Required Sample Size (Completed / Evaluable)	24
Estimate Participant Drop Out / Withdrawal after Randomization/Inclusion	4 (17%)
Total Required to Randomize / Include	28
Estimate Participant Screen Fail / Exclusion	12 (30%)
Total Required to Consent	40

478
 479 7.4.2. Primary (i.e., primary outcome variables) and secondary endpoints
 480 **Health Questionnaire and Self-Report Measures:** The primary aim of this pilot is to explore the potential feasibility,
 481 safety, and effect of CBD in reducing PTSD symptoms compared to placebo in retired service members receiving mPE.
 482 Therefore, the primary outcome variables will be the CAPS-5 total score, the PCL-5 total score, and adverse event

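### Sections 7.1 and 7.4.1 randomise 28 to obtain 24 completers, but the abstract randomises 24 and Section 7.3 has study drug prepared for only 24

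*Combined protocol and SAP*

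**What the plan says.** Two sections set out the recruitment numbers in full, and they agree.

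- Section 7.1 lists 40 to be screened, then "Target number randomized: 28" and "Target enrollment number for completers: 24".
- The Section 7.4.1 table gives 24 against "Estimate Required Sample Size (Completed / Evaluable", 4 (17%) against "Estimate Participant Drop Out / Withdrawal after Randomization/Inclusion", and 28 against "Total Required to Randomize / Include". It also gives 12 (30%) screen failures and 40 to consent.

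Two other places carry a different number.

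- The abstract (Section 2) says the study will "enroll 24 individuals with PTSD to be randomized to CBD (n=12) or placebo (n=12".
- Section 7.3, in the paragraph on study drug, has the pharmacy obtain "CBD for 12 participants from their supplying manufacturer" and then prepare 12 active and 12 placebo sets, as "dosage for 24 participants in blinded containers that will be numbered per the randomization design".

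Aim 1, Section 6 and the Section 11.0 timeline also use 24. Their wording does not say whether those 24 are people randomised or people who complete. I found no provision for replacing dropouts, reusing container numbers or preparing more supply later.

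**The concern.** The number randomised is a working figure. It sets the length of the randomisation list and how many numbered containers the pharmacy makes. Because Section 7.4.3 makes the analysis intent to treat, it also defines the analysis set. Under Sections 7.1 and 7.4.1 that set is 28; under the abstract it is 24.

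A pharmacy working from Section 7.3 would prepare for fewer people than Sections 7.1 and 7.4.1 intend to randomise. A team working from the abstract would stop randomising at 24 and, on the plan's own loss, would not reach 24 completers. Feasibility is a main interest of this pilot, so a completer shortfall produced by the document itself would be awkward to interpret.

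**Working it through.** **Inputs.** From Section 7.4.1: 24 completers, 4 lost after randomisation (printed as 17%), 28 to randomise, 12 screen failures (30%), 40 to consent. From the abstract: 24 randomised, 12 per arm. From Section 7.3: containers for 24 (12 active, 12 placebo). From Section 6: 1:1 allocation in blocks of four.

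**1. The plan's own figures.** 40 − 12 = 28 and 28 − 4 = 24. Also 12/40 = 30%. Sections 7.1 and 7.4.1 reproduce exactly.

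**2. The 17% label.** 4/24 = 16.7%, so the printed percentage is taken on completers. The row describes loss after randomisation, for which the base is 28: 4/28 = 14.3%. If 17% really were the share lost among those randomised, the requirement would be 24/(1 − 0.17) = 28.9, or 29. The counts are therefore sound and only the percentage is mislabelled.

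**3. If 28 are randomised.** Containers described minus people randomised: 24 − 28 = −4. With an even 14:14 split that is 14 − 12 = 2 short in each arm.

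**4. If 24 are randomised.** Expected completers:
- at a loss of 4/28: 24 × (24/28) = 20.6
- at a loss of 17%: 24 × 0.83 = 19.9

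To finish with 24 completers from 24 randomised, nobody may be lost. With independent losses the chance of that is (24/28)^24 = 2.5%, or 0.83^24 = 1.1%.

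**5. Can 24 mean completers everywhere?** The abstract attaches its 24 to the act of randomisation. In Section 7.3 the containers are numbered from the randomisation design and given out at the medication review, three days before therapy begins. Completion cannot be known then, so supply has to match the number randomised. The completer reading fails in both places. It remains possible for Aim 1, Section 6 and the timeline, which I treat only as supporting evidence.

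**6. Effect on precision.** For an unadjusted two-group comparison with Hedges' g near 0, the approximate 95% half-width is 1.96 × √(2/n), with n per arm.

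| Who supplies the outcome | 24 randomised | 28 randomised |
|---|---|---|
| Everyone randomised | n = 12: 0.80 | n = 14: 0.74 |
| Completers only (about 20 or 24 in all) | n = 10: 0.88 | n = 12: 0.80 |

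The difference is 0.06 to 0.08. It does not describe the planned mixed model, which also uses data collected during treatment.

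**The case against.** The strongest reply is that the design number is not in doubt. The two sections that set out recruitment both say 28, they agree to the last participant, and a summary sentence and a supply sentence were simply not aligned with them. Much of this stands. It is a problem of consistency between sections, the calculation is correct, and the pilot is expressly not powered for efficacy. It does not remove the conflict, because the supply sentence is the one a pharmacy would act on and nothing in the protocol says it is provisional.

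Some stronger readings are tempting but lack support.

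- A reader might infer that the protocol repeatedly states 24 randomised. Only the abstract does. Section 7.3 conflicts by implication, through its supply figure, and the other uses of 24 may mean completers.
- A reader might infer a shortfall well above four, because blocks of four are opened in four strata. If every opened block were prepared in full within its stratum, up to three containers per stratum could go unused: 28 + 4 × 3 = 40 at most. The same allowance arises with 24 randomised (24 + 4 × 3 = 36), so it is a separate matter. The documents state no such preparation rule, nor that all containers are made at once; Section 6 has a coordinator work with the pharmacy on blocking.
- A reader might infer a recruitment overrun: 28 at two per month takes 14 months, against 12 scheduled (months 4 to 15). Section 11.0 does not say that its rate counts people randomised. If it counts completers, 24/2 = 12 months fits.
- A reader might take 0.80 versus 0.74 as the cost in precision. That assumes no outcome is lost. The Section 7.3 schedule has CAPS-5 only at baseline and one month, so people who drop out may lack it, although the final evaluation in Section 10.0 may recover some data.

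**Conclusion.** The inconsistency is real and should be corrected. The number randomised is 28 in Sections 7.1 and 7.4.1 and 24 in the abstract, and the supply in Section 7.3 matches 24. The shortfall is at least four containers if 28 are randomised. The alternative is about 20 completers in place of the stated 24 if 24 are randomised. The first figure is simple subtraction; the second assumes the plan's own loss rate applies. Precision changes little under either assumption about missing outcomes, no power figure is affected, and the design is not invalidated. The 17% label is a minor matter beside this.

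**What to change.** Use one randomised number throughout. Either option resolves the conflict.

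- **Keep 28.** State 28 randomised, about 14 per arm, in the abstract. Size the randomisation list and the Section 7.3 supply to at least 28. Label 24 as completers in Aim 1, Section 6 and the Section 11.0 timeline. Relabel the loss in Section 7.4.1 as 4/28 = 14%. Cost: wording and study drug or placebo for at least four more participants.
- **Keep 24.** Leave the abstract and supply text as they are, set the number randomised to 24 and expected completers to about 20 in Sections 7.1 and 7.4.1, and revise the related rows of the table to match. Cost: wording, a lower completer number, and an interval wider by about 0.06 to 0.08 in half-width than with 28.

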- 322 • Location where study product(s) will be stored: The medication will be received from Oakdell Pharmacy by a 323 trained study team member and transported to the STRONG STAR clinic where it will be stored in a locked 324 cabinet until the participant arrives to receive the medication at the medication review appointment.
- 325 • Dose range, schedule, and administration route of study product(s): 2.5 mL (250mg) taken twice daily in the 326 morning and evening after meals for (500mg per day) for 18 consecutive days beginning three days prior to the

327 start of mPE. Epidiolex and placebo will be prepared by Oakdell Pharmacy in a strawberry-flavored liquid solution
 328 administered using an oral syringe.

329 • Plan for disposition of unused study product(s): Any unused study products will be disposed of in accordance with
 330 the STRONG STAR Drug Accountability and Storage SOP.
 331 • FDA status: The FDA has approved the use of Epidiolex for seizure disorders. Prior research has demonstrated
 332 the safety and early positive benefits of off-label use of Epidiolex for Anxiety and Trauma-Related symptoms in
 333 humans. We are not seeking a new indication with this research project.

334 7.3. Research Interventions/Study Procedures.

335 **Interventions.**

336 Participants will be randomized to either Epidiolex (CBD) or placebo. All participants will receive 10 sessions of mPE
 337 administered weekdays over 2 weeks.

338 Epidiolex (CBD) is an FDA approved, non-controlled prescription medication indicated for the treatment of seizure
 339 disorders. Prior research has demonstrated the safety and early positive benefits of off-label use of CBD for Anxiety and
 340 Trauma-Related symptoms in humans. CBD comes in a 100-mL bottle containing 100 mg of CBD per ml of strawberry-
 341 flavored liquid solution that is taken using an oral syringe. Strawberry-flavored liquid solution is also available for Oakdell
 342 pharmacy to create a comparable placebo to maintain the blind. Starting recommended dose is 2.5 mL (250mg) taken
 343 twice daily (total = 5 mL/500mg) in the morning and evening after meals.¹ We will employ this dosing recommendation for
 344 this study for 18 consecutive days. Steady state has been shown to occur in 2 days.⁴¹ To ensure maintenance on an
 345 adequate steady state dose for all randomized participants, we will begin medication 3 days prior to the start of mPE. CBD

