367 **Study Procedures.**

Study Procedure	Visit / Follow Up (F/U) Interval										
	Base-line	Medi-cation Review* (Day 1)	PE 1	PE 2	PE 3-4	Interi m Asses s (PE 5)	PE 5-9	Interi m Asses s (PE 10)	PE 10	18 days following medicatio n review	1 Month from completio n of treatment Follow-up
Study Days		1	4	5	6-7	8	8, 11-14	15	15	18	45
Informed Consent	R										
1. Demographics and Military Service Characteristics Form	S,R										
2. Life Events Checklist-5	S,R										
3. Deployment Risk and Resilience Inventory-2	S,R										
4. STRONG STAR Health Questionnaire	S,R										R

5. Prior and Concomitant Medications Interview	S,R									
6. Self-Injurious Thoughts and Behaviors Interview short form	S,R									R
7. Depressive Symptom Index – Suicidality Subscale	S,R		R			R		R		R
8. Clinician-Administered PTSD Scale for the DSM-5(CAPS-5)	S,R									R
9. PTSD Checklist for the DSM-5 (PCL-5)	R		R			R		R		R
10. Patient Health Questionnaire-9	S,R		R			R		R		R
11. Generalized Anxiety Disorder-7	R		R			R		R		R
12. Brief Inventory of Psychosocial Functioning	R									R
13. Veterans RAND 12 Item Short Form Health Survey	R									R
14. Quick Drinking Screen	S,R									R
15. National Institute of Drug Abuse-Quick Screen	S,R									R
16. Insomnia Severity Index	R									R
17. Posttraumatic Cognitions Inventory	R		R			R		R		R
18. Credibility and Expectancy Questionnaire for PE				R						
19. Credibility and Expectancy Questionnaire for CBD				R						
20. AEA, 2-AG (Blood Draw Collection)		R	R			R		R		
21. Cortisol (Saliva Collection)		R	R			R		R		
22. HR Monitoring During Exposure (PE 3, 5, 10)					R		R		R	
23. Adverse Event Monitoring		R**	R	R**	R**	R	R**	R	R**	R**
24. Urine Pregnancy/Drug Screen	S									
25. Liver Function Tests Labs*(LFTs)	S									
26. Massed Prolonged Exposure			R	R	R		R		R	
27. CBD 500mg/daily or placebo daily*		R _{start}	R	R	R		R		R	R _{end}

Table Notes. S=screening purposes; R= Research purposes; *Medication Review Appointment will occur three days prior to beginning Massed Prolonged Exposure. Start and End superscripts represent beginning and end of medication/placebo use. CBD=Cannabidiol; AEA=Anandamide; 2-AG=Arachidonoylglycerol; HR= Heart Rate; *All potential study candidates will be required to complete LFTs or provide a copy of recent LFT labs (completed within 90 days of baseline) and bring their lab results prior to randomization.

*CBD or placebo to be administered daily days 1-18.

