** Daily Adverse Event monitoring to occur if participant taking one of the identified medications warranting additional monitoring. See Section

372

373

7.3.1 Collection and Storage of Human Biological Specimens.

374

Urine drug and pregnancy screen tests will be conducted at baseline for screening eligibility purposes.

375

376

Blood will be collected at four time points for a study total of about 28mLs. Approximately, 7mL of blood will be collected by venous puncture using a 7 mL EDTA blood collection tube immediately prior to the pretreatment medication review, and at interim assessments 1 (prior to PE session 1), 2 (prior to PE session 5), and 3 (prior to PE session 10). Blood will be immediately chilled in a cooler filled with ice.

377

378

379

380

Saliva will also be collected at four time points via passive drool. At the medication review appointment participants will be given a kit with salivette test tubes and instructions on how to collect early waking saliva samples (cortisol) upon waking. Saliva collections will be completed upon waking the day after the medication review appointment, and the day of sessions 1, 6, and 10. Participants will be instructed to immediately refrigerate the sample and bring it to the next scheduled appointment. Saliva samples will be collected from the participant by study staff when the participant arrives for their appointment and immediately chilled in a cooler filled with ice. Samples will be frozen at or below -20°C upon arrival at the Biological Psychiatry Analytic Laboratory (BPAL).

381

382

383

384

385

386

387

388

389

390

391

392

393

394

395

396

397

398

399

400

Biological specimens will be coded when collected from the participant by the study staff with a digital bar code that can be linked to the study and subject only by key-codes maintained by the STRONG STAR Data and Statistics Services.

Heart rate will be monitored using a wearable device placed on the right wrist, and elevations will be recorded continuously during sessions 3, 6, and 10 to obtain an objective measure of arousal to assess possible within- and between- session extinction learning in response to rehearsal of the individual's primary traumatic event. This data can be beneficial for individuals who report subjectively being more aroused during the exposure or behaviorally appear to be more activated.

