All biospecimen samples will be transported to the BPAL in the UTHSA Department of Psychiatry and Behavioral Sciences at the UT Health-Long School of Medicine in room 727F for processing and storage. This location is monitored 24-7 by a wireless monitoring system on the Isensix system.

401 402 7.3.1.1 Laboratory evaluations and special precautions:

403 All biospecimen collection procedures will be carried out by trained team members and appropriately transported, stored,
404 and disposed of in accordance with STRONG STAR Biomarkers and Genomics Services SOP, International Air Transport
405 Association (IATA), and UTHSA IRB guidelines. All samples will be labeled with coded subject numbers and dates to
406 protect the identities of participants.

407 At the times designated in Section 7.3 Table, 7mL of venous blood will be drawn into one purple top tube for
408 measurement of AEA, 2-AG, and CBD levels. Immediately upon collection, blood will be labeled, mixed, and chilled on
409 ice. This blood will be transported to the BPAL as soon as possible, where it will be processed to separate out the plasma.
410 Plasma will be aliquotted into two cryovials, labeled, and placed in the STRONG STAR-CAP biorepository for long-term
411 storage at -80° C. Samples will be later analyzed in batches using HPLC/Tandem Mass Spectrometry.

412 On the days designated in Section 7.3 Table, saliva samples will be collected by participants immediately upon awakening
413 in the morning. Samples are collected by passive drool saliva collection into saliva sample tubes labeled only by coded
414 subject number and Day number. Participants will be instructed to refrigerate the sample upon collection and to bring the
415 salivette to their next scheduled appointment. Saliva samples will be collected from the participant by study staff when the
416 participant arrives for their appointment and immediately chilled in a cooler filled with ice and then brought to the BPAL for
417 storage at -20° C as soon as possible. Subjects will bring these samples to their visit appointment and staff will receive
418 them and transport them to the BPAL for long-term storage until later analysis for cortisol levels.

419 420 7.3.2 Data Collection.

421 See Table in Section 7.3 for a summary of the assessments and timing of administration. The data collected in the study
422 will be coded using an assigned number. Hard copies of data collected during the study will be securely stored in locked

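### No workable saliva cortisol sample precedes the first dose, and the text and table disagree on the mid-treatment session

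*Combined protocol and SAP*

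**What the plan says.** **First saliva sample.** Section 7.3.1 says "At the medication review appointment participants will be given a kit with salivette test tubes", and then: "Saliva collections will be completed upon waking the day after the medication review appointment, and the day of sessions 1, 6, and 10".

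**Start of dosing.** Under Section 7.2.1 the product is kept in a locked "cabinet until the participant arrives to receive the medication at the medication review appointment". It is taken "morning and evening after meals for (500mg per day) for 18 consecutive days beginning three days prior to the" start of therapy. The notes to the table in Section 7.3 add "CBD or placebo to be administered daily days 1-18", and row 27 of that table carries its start mark in the Day 1 column.

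**Table and laboratory section.** Row 21 of the table (cortisol) is marked at the medication review (Day 1), PE 1 (Day 4), the PE 5 interim assessment (Day 8) and the PE 10 interim assessment (Day 15). Section 7.3.1.1 follows the table: "On the days designated in Section 7.3 Table, saliva samples will be collected by participants immediately upon awakening".

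**Blood, for comparison.** The AEA and 2-AG draws are taken "immediately prior to the pretreatment medication review, and at interim assessments 1 (prior to PE session 1), 2 (prior to PE session 5") and 3, before session 10.

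**Use of cortisol.** Hypothesis 4 compares cortisol levels between arms following treatment. Hypothesis 6 relates cortisol reduction to symptom reduction. Section 7.4.3 plans Pearson correlations involving change in symptoms, biochemical markers and physiology.

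**The concern.** A change score for a drug-responsive marker needs a starting value taken before the drug. Blood has one, and PCL-5 and CAPS-5 have a baseline value. As scheduled in Section 7.3.1, cortisol does not. In the CBD arm the first sample follows exposure to CBD; in the placebo arm it follows placebo only. A cortisol change for Hypothesis 6 would therefore start after dosing, while the AEA, 2-AG and symptom changes it is set beside can start before it.

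The text and the table also put the mid-treatment saliva sample at different sessions. If staff follow the text, mid-treatment cortisol is separated from mid-treatment AEA and 2-AG, because blood is at session 5 in both places.

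**Working it through.** **1. Study days.** From the table in Section 7.3: review on Day 1; PE 1 to PE 4 on Days 4 to 7; PE 5 on Day 8; PE 6 to PE 9 on Days 11 to 14; PE 10 on Day 15. Medication starts three days before PE 1, so on Day 4 − 3 = Day 1. Eighteen consecutive days then end on Day 18, which reproduces the table note. A Day 2 start would end on Day 19 and would not match.

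**2. Doses before each saliva sample.** With twice-daily dosing, the number of scheduled doses before waking on Day d is 2(d − 1) if Day 1 includes a morning dose, and 2(d − 1) − 1 if dosing starts that evening. The documents do not give the clock time of the first dose.

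| Sample | Day | Scheduled doses before it |
|---|---|---|
| First (7.3.1) | 2 | 1–2 |
| Session 1 | 4 | 5–6 |
| Mid-treatment, session 6 (7.3.1) | 11 | 19–20 |
| Mid-treatment, session 5 (table) | 8 | 13–14 |
| Session 10 | 15 | 27–28 |

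So 0 of 4 saliva samples are pre-dose, against 1 of 4 blood samples.

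**3. Can the table's Day 1 mark supply a pre-dose sample?** Read with Section 7.3.1.1, it asks for a sample on waking on Day 1. The kit is first issued at the appointment later that day, so the sample cannot be taken as written. Text and table both count four samples, so the Day 1 mark most plausibly is the text's Day 2 sample.

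**4. Effect on a difference in change.** Let D2 and D15 be the cortisol differences, CBD minus placebo, on Days 2 and 15. Change measured from the first sample gives D15 − D2. Change from a pre-dose sample would give D15 − 0 in expectation, by randomisation. The shift is therefore −D2, and the share of D15 that remains is 1 − D2/D15. The documents give no cortisol time course, so the ratios below are assumptions.

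| D2/D15 (assumed) | Share of D15 remaining |
|---|---|
| 0 | 100% |
| 0.25 | 75% |
| 0.5 | 50% |
| 1 | 0% |

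The direction of any effect on the Hypothesis 6 correlation cannot be determined from the documents.

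**5. Hypothesis 4 precision.** The comparison of levels stays unbiased by randomisation, but there is no pre-dose value to adjust for. With 12 per arm and no covariate, the 95% CI half-width is t(0.975, 22) × √(2/12) = 2.074 × 0.408 = 0.85 SD. With a covariate correlated ρ with the Day 15 value, it is t(0.975, 21) × 0.408 × √(1 − ρ²):

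| ρ (assumed) | Half-width | Narrower by |
|---|---|---|
| 0.3 | 0.81 SD | 4% |
| 0.5 | 0.74 SD | 13% |
| 0.7 | 0.61 SD | 28% |

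These figures ignore chance imbalance in the covariate; allowing for it brings the gains to about 2%, 11% and 27%.

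**6. Session conflict.** Saliva is on Day 11 in the text and Day 8 in the table, three days apart, for 1 of 4 samples. Heart rate is at sessions 3, 6 and 10 in Section 7.3.1, but at PE 3, 5 and 10 in the label of table row 22. The heart-rate mark itself sits in the PE 5–9 column, which covers both sessions, so that conflict is with the label only.

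**The case against.** The table and Section 7.3.1.1 together do schedule a Day 1 waking sample, which would be pre-dose because medication is handed over only at that day's visit. On this view the documents are inconsistent rather than lacking a baseline by design. That is fair as a description, but the sample still cannot be collected with a kit not yet issued, so a participant handled as Section 7.3.1 describes has no pre-dose value.

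The harm also depends on choices the plan leaves open, and much of this stands:

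- Section 7.4.3 does not name the start and end samples for change, does not name cortisol among the mixed-model outcomes, and does not plan a baseline covariate.
- The Day 2 sample precedes all therapy sessions, so it remains a pre-therapy reference.
- If D2 is zero, the Day 2 value can serve as the covariate and little or no precision is lost.
- The ratios and correlations are illustrative and say nothing specific about this trial.
- With 14 per arm (28 randomised) the unadjusted half-width is 0.78 SD rather than 0.85.

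These points limit the size of the consequence. None of them supplies the missing sample, and it cannot be recovered afterwards.

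**Conclusion.** Both parts hold. As the saliva procedure is written, every cortisol sample follows at least one scheduled dose, and the mid-treatment sample has two incompatible dates. What is lost is each participant's pre-dose cortisol reference, and with it the possible adjustment for Hypothesis 4.

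The scheduling facts are firm. The size of the consequence is not: it depends on D2, which the documents do not give and which may be zero. Exposure to CBD at the first sample concerns the CBD arm only, 12 of the planned 24.

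The point is minor. It affects exploratory aims in a pilot that Section 7.4.3 says is not powered for mechanistic testing, and the primary outcomes are untouched.

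**What to change.** Issue the saliva kit before the medication review, either at the baseline visit or once eligibility is confirmed. Take the first sample on waking on the morning of the review, before medication is received, and hand it in at that visit. This matches the pre-dose blood draw and makes the table's Day 1 entry feasible. It also avoids keeping the Day 2 sample at home until the next visit in the table, on Day 4.

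If this is not adopted, state in Sections 7.3.1 and 7.4.3 that cortisol has no pre-dose sample and that cortisol change starts after dosing.

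Separately, reconcile Section 7.3.1, Section 7.3.1.1 and the table on one mid-treatment session for saliva, and reconcile the heart-rate row label with Section 7.3.1.

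The cost is small: wording changes, no added assays and no change to dosing. Issuing at baseline uses up to 40 − 28 = 12 extra kits (consented minus randomised). It also needs another contact for participants whose baseline testing is carried over from a different study, which Section 7.1.5 allows. Issuing once eligibility is confirmed needs no extra kits. It fits the hand-in of liver test results before randomisation if the candidate attends in person; otherwise a separate hand-over is needed.
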